hybrid intervention (H3b), data during the hybrid treatment period will be compared to within-person outcome data during the wait period. Moreover, we will compare hybrid treatment participants to all BA and THR participants. For both hypotheses 3a and b, LMM models similar to the one for Aim 1 efficacy analysis will be used. Again, the between-group difference in outcome change between baseline and 10 weeks will be used to assess efficacy and tested for statistical significance. The 95% confidence interval for efficacy and corresponding effect size (Cohen's D) will be reported. Any imbalanced confounding variables will be adjusted in the model. To explore whether THR effects are any different between participants recently discharged from the psychiatric hospital and those without recent psychiatric hospitalization, we will compare THR effects between these two groups of THR/BA participants by introducing three extra terms in the model for Aim 1. They include an indicator variable (RecentHosp) for this sub-classification (with or without recent hospitalization) and the intervention*RecentHosp and intervention*RecentHosp*time interaction terms. Contrasts will be set up to test the effect of interest and 95% CI for this effect assessment will be calculated

Power analysis: Because significant intervention effect is the prerequisite of mediation analysis, this study is powered primarily on analyses of the primary outcome, ABC-C irritability. For the primary efficacy analysis at T2, effect sizes were estimated for the primary outcome (ABC-C irritability) based on data from our THR RCT¹³ among participants who had psychiatric diagnosis (N=27 for THR and N=26 for BA, data not published). The irritability score decreased by 6.9 (1.66 SEM) in the THR group and 2.3 (1.8 SEM) in the BA group, resulting in a Cohen's d of 0.62 for efficacy. We will enroll 142 participants (71 per arm). To allow for 20% attrition (which is 1% higher than that in our previous trial) at T₂, the sample size for completer or mediation analysis would be 56 per arm. In this case, we will have 97% power at 5% significance to detect significance of THR efficacy for ITT analysis (Aim1) and 90% power for completer analysis. For the mediation analysis, our previous data indicate that the standardized coefficient for the total effect (path c) is 0.34. There are no previous data available for estimating coefficients for paths a and b. We assume that both coefficients are of medium effect size¹³⁷ and the indirect path will explain half the total effect. That is, $a \times b = 0.17$ (e.g., $a=0.4$, $b=0.43$). In this case, a total sample size of 112 provides 90% power at 5% significance to detect a significant indirect effect. This power estimate is based on the Sobel test and was calculated by the R package, power Mediation. **Table 2** shows the power for analyzing secondary and exploratory outcomes at T₂ if the ES is similar to those from data in our previous RCT. (Based

TABLE 2		Power at 5% significance	
Power from ES	ITT (n=81/arm)	Completers (n=56/arm)	
ABC-C Irritability	97	90	
ABC-C Hyperactivity	94	83	
SRS Social Cogn.	92	80	
SRS Social Comm.	>99	>99	
SALT # diff. words used	>99	>99	
SALT # words used	>99	>99	

on 18 THR and 11 BA, participants with concomitant psychiatric diagnosis and six-months follow-up ABC-C data from our RCT, the ES for THR effect on the six-month irritability score was 0.45 (not published) as compared to BA participants. In this case, we will have 81% power for the primary ITT analysis (n=81 per arm) to detect the THR effect on ABC-C, but 56% power to see statistical significance for completer analysis. This analysis assumes that 45 participants per arm will be followed six-months after the intervention. Aim 3 is more hypothesis generating and exploratory. 20 extra participants will be enrolled in the wait list group who subsequently received Hybrid intervention. To minimize the imbalance between groups, we will randomize with 1:1:1 ratio the first 60 Colorado participants into BA/THR/wait list group. The minimum detectable effect size needs to be 0.9 (0.74) Cohen's D to have 80% power if 20 wait list (or Hybrid) participants

will be compared to 20 (or 56) other participants.

Supplementary analyses: 1.) It is likely that participants will have changed psychoactive medication during the 10- week intervention period and this change is not balanced between two study arms. History of medication change for each participant will then be documented and characterized into few categories, as appropriate. This category of medication change (to be determined) will be introduced into the statistical models for Aims 1 and 2 to adjust for their potential confounding effect for efficacy and mediation analysis. 2.) to examine the effect of intervention sites (Colorado or Maine), we will tabulate the effect size of THR effect by site and introduce site and site by intervention terms into the models mentioned above for efficacy analysis in order to statistically test the site by intervention interaction effect. 3.) We will explore factors that related to the response to THR intervention traditional variable-centered and the state-of-the-art person-centered methods. We will classify each THR subject as responder or non-response (with criteria to be determined) and use logistic regression to identify baseline demography factors and clinical factors (such as psychological diagnosis) that are associated with the response. Moreover, latent profile analysis will be used to group all the participants into few clusters who share similar demography and baseline clinical characteristics. Difference in intervention effect will be examined across these clusters to determine who are more responsive to the intervention. In the later analysis, the outcome will be change score after intervention, the model will consist of cluster, treatment and their interaction. Test of interaction is of primary interest. 4.) In our previous R01 THR study, we observed that the intervention (Barn or THR) reached it.

Summarize Knowledge to be Gained:

Our proposal aims to move the HAI field beyond efficacy trials, specifically regarding THR:

The experiments outlined in this application are designed to move the HAI field forward to provide evidence to begin to answer the more nuanced questions of **how** it works, **for whom** does it work and for **how long**, as well as **under what conditions** (dose) does it work. The historical theoretical focus on HAI leading to arousal regulation/conditioning is an ideal target for mediation analyses via physiological measurement. The knowledge to be gained from this proposal will provide evidence for physiological response patterns as a causal pathway to THR outcomes and has the potential to guide future researchers who wish to explore mechanisms by which HAI demonstrates benefits beyond THR and to other populations.

Aim 1 addresses the call to identify “causal relationships” and evaluate the “community-level and social benefits” of HAI, as identified by the PAR 18-213 HAI funding announcement. The proposed ASD study population tends to have atypical arousal response profiles, particularly youth with ASD and psychiatric diagnoses, making them more likely to benefit from an intervention such as THR whose outcomes may be mediated by physiological arousal regulation benefits. In line with the NIH RDoC framework,⁹³ elucidating physiological pathways influenced by THR in ASD may also suggest how THR could be useful for other psychiatric populations where similar psychophysiological pathways are known to be impaired. We also propose to expand our outcome measures to include evaluation of wider ranging benefits of THR, as children with ASD are at high-risk for behavioral disturbances that can impair their QOL as well as their caregivers. National surveys and studies indicate higher rates of caregiver stress and frustration related to the care and management of behaviors of children with ASD compared to other special needs populations,^{7,8} suggesting this is a critical outcome to measure multidimensionality, including caregivers’ physical, mental, and social well-being.⁹⁴ We propose to use the *World Health Organization’s Quality of Life Instrument (WHOQOL-BREF)*⁹⁵, which is used for a variety of populations, including ASD, to provide an index to measure caregivers’ adjustment.⁹⁴ Our inclusion of this standardized QOL measure will allow us to broaden the understanding of HAI efficacy to other research disciplines as well as understand the impact of THR on caregivers QOL. Problems with emotional dysregulation are present in other psychiatric populations (e.g., anxiety and mood disorders) and not specific to the ASD population.³⁷ Our inclusion of a distinct outcome measure of ER that is sensitive to change, quantifies variability in emotion dysregulation, has been validated for use with an ASD population with a variety of ability levels, and has the potential to generate information needed for follow-up studies broadens examination of THR as a potentially effective transdiagnostic intervention.

Aim 2 determines if THR outcomes are maintained over time. We propose to address the paucity of HAI research examining long-term maintenance of effects. In addition to our six-month follow-up report¹⁸ in a subset of participants in our THR RCT¹³, to our knowledge, only one other study to date has attempted to prospectively examine residual effects of THR in children with ASD, but it had several methodological limitations including teacher-report measures, lack of a control condition, and an unplanned six-week break during the initial treatment phase.⁹⁶ Information on longer term THR effects has important clinical practice implications, including the possibility that THR could be an adjunctive intervention to the current practice of using psychotropic medications to reduce symptoms of aberrant behaviors in ASD youth.⁷⁴

Aim 3 explores dose and sub-population effects of THR and Barn Activity (BA) interventions. This aim addresses important next steps to advance the HAI field of research. A recent systematic review of HAI research with the ASD population discussed the field’s tendency to employ diverse research methods that lack replication and use of non-homogenous ASD samples, which limits the ability to determine who might benefit the most from HAI and under which conditions.⁷¹ Exploratory analyses of our RCT¹³ sample showed stronger positive outcomes in the subgroup of THR participants with co-occurring psychiatric disorders, which provides support to focus on this group who stands to benefit the most from THR. Additionally, the BA no-horse control group in our RCT¹³ showed significant within-group improvements in irritability and hyperactivity behaviors at the conclusion of the intervention, but we were unable to draw conclusions about the effects of that BA group due to the absence of a nonintervention control. Thus, we aim to both explore the effects of BA compared to a waitlist control and explore the dosing effects of a Hybrid group (i.e., 5 weeks BA followed by 5 weeks THR).

Our project design is an innovative approach that will provide ground-breaking advancements in the HAI field (specifically THR). Our approach innovates by: conducting a large RCT targeting a majority subset of the ASD population, who have indications of being potentially stronger THR responders⁹⁹; using an intervention manual for both experimental and control conditions and measuring their fidelity to ensure implementation uniformity, specifically accounting for effects of the horse while controlling for social attention throughout the study; including a method to understand the six-month maintenance of THR outcomes vs. a control; and implementing the study in two community-based rural settings to expand the ecological validity of our manual-based THR intervention.¹⁶

We are grounding our mediation analysis in the framework of a model to be tested using a RCT.

Methodologically, including multiple physiological measures will allow us to decrease the biasing effects of measurement error⁵⁸ and more systematically assess whether positive THR outcomes are partially accounted for by physiological response profiles over time in youth with ASD and co-occurring psychiatric diagnoses.

Our measurement approach is technically innovative. Our proposal seeks to employ objective measures of participants' experiences by using unobtrusive state-of-the art, ambulatory physiological measures during an HAI activity to capture the potentially complex profile of mediating factors that may explain previous outcomes. Our methodology takes advantage of technological advances in wearable physiological biosensors that overcome the inherent difficulty obtaining reliable self-reports on emotional and physiological states in individuals with ASD, a portion of whom are either minimally-verbal or have alexithymia.¹⁰³⁻¹⁰⁵

References:

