Specific Aim 3: Explore dose and sub-population effects of THR and BA interventions by comparing effect size differences in THR and BA groups to a (1) 10-week wait-list control group (n = 20); (2) Hybrid intervention group (n = 20) (five weeks BA followed by five weeks THR); and (3) most severely impaired subsample (n = 20) of the THR study population randomized following psychiatric hospitalization. *H3a. The BA group will show significantly greater improvements on Aim 1 outcomes compared to those randomized to the waitlist control group. H3b. The Hybrid group will show a similar response pattern as the THR group.*

Specific Aim 4: Explore anecdotal observations of the study intervention personnel (i.e. instructors and volunteers) by providing study intervention personnel with a written survey of questions to gather information about their study observations and experiences. *H4. The written reflections of study personnel about their interaction with the study population will provide anecdotal support for the study findings.*

Our preliminary data demonstrate that physiological data collection is feasible with ASD youth engaged in THR at the proposed PATH international ¹⁷premiere accredited riding centers: (1) northern Colorado where access to psychiatric care is limited and (2) Portland, ME near a specialized ASD psychiatric hospital program. We also partially replicated our previous results, demonstrating cortisol is a viable target mediator of THR effects on aberrant behaviors in ASD youth.¹⁸ Our team has collaborated across the two study sites for over five years and has the necessary clinical and technical experience to conduct this next phase of THR research.

Background and Significance:

ASD population with co-occurring psychiatric disorders

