Emotion Dysregulation Inventory (EDI)^{128,129} The EDI was developed to assess ER impairment in ASD following guidelines from the NIH Patient-Reported Outcomes Measurement Information Systems (PROMIS) initiative, and its final items were based on factor analyses and item response theory (IRT) analyses using data from 1,755 youth with ASD. The EDI is a 30-item caregiver-report form that includes a 24-item Reactivity item bank, which captures intense, rapidly escalating, sustained, and poorly regulated negative emotional reactions, and a six-item Dysphoria scale characterized by minimal positive affect and motivation, and the presence of nervousness and sadness. Both the Dysphoria Scale and a seven-item Reactivity Short Form have IRT-based theta scores, which have a mean of 0 and SD of 1, and provide superior discriminative ability to raw scores.¹³⁰ Validity evidence includes expected group differences (higher scores in an ASD psychiatric inpatient versus community sample), correlations with measures of related constructs, and demonstration of test-retest stability.

*World Health Organization's Quality of Life Instrument (WHOQOL-BREF)*⁹⁵ is a widely used measure of patients' and caregivers' QOL. It has cross-cultural validity and strong psychometric properties (good discriminant, content, and test-retest validity). It is a 26-item measure that assesses the impact of the child on the caregiver's QOL in four domains (physical, psychological, social, and environmental). Test-retest reliability is good for the four domains (Cronbach alpha 0.66-0.84).⁹⁵ This tool was validated in parents of children with ASD and shows promise as being sensitive to unique challenges faced by parents of children with ASD.⁹⁴

Crisis Mental Health Care Usage Survey is a list of questions developed by the Autism Developmental Disabilities Research Collaborative (ADDIRC) pertaining to the participant's need for crisis care services within 2 ½ months before starting the study, at the end of the 10-week study intervention period, and 6 months after the study intervention period. Survey questions include psychiatric hospitalization (inpatient or partial), in-home crisis evaluation/management by police, behavior specialist or social services, or mental health related emergency room visits.

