Setting: To address Aims 1 and 2, all THR and BA control interventions and physiological data collection will take place at two Premiere accredited PATH¹⁷ international therapeutic riding centers: (1) Colorado: Hearts and Horses in Loveland and (2) Maine: Riding to the Top Therapeutic Riding Center in Windham. Note: study consent/assent and initial screening visits will occur at the following sites: Children's Hospital Colorado main campus and satellite clinic site locations, Colorado State University, and Maine Behavioral Healthcare/Center for Autism and Developmental Disorders clinic (CADD). The Colorado site is a large facility that has previously participated in our replication pilot¹⁸ and is located in a rural area that draws referrals from northern Colorado and southern Wyoming where intervention resources are limited for youth with ASD who require extensive services to address psychiatric issues and related aberrant behaviors. The Colorado site will also recruit participants for the waitlist/hybrid groups to address exploratory Aim 3a & 3b. The Maine site is located in close proximity to a large inpatient and outpatient psychiatric treatment center for youth with ASD in Portland (Maine Behavioral Healthcare/Spring Harbor Hospital). Therefore, the Maine site will also recruit ASD youth psychiatrically hospitalized at Spring Harbor Hospital to address exploratory Aim 3c. Please note Maine site is closed as of December 31, 2023.

Recruitment: IRB-approved study recruitment materials will be used for participant recruitment in communities (i.e., schools, ASD parent-support networks, and service agencies) near each of the two therapeutic riding centers. The Maine Site will recruit participants discharged from Maine Health's Spring Harbor Hospital's inpatient and partial psychiatric unit. At the Colorado site, participants will also be recruited via the COMIRB-approved study flier sent through Children's Hospital Colorado MyChart EPIC messaging system.

Pre-screening: Pre-screening will take place via REDCap survey or phone interview. Pre-screen questions are the same regardless of modality. Pre-screen questions are specific to study inclusion and exclusion criteria previously described. Those meeting initial pre-screening inclusion criteria will be scheduled for an initial screening visit at their respective locations (Children's Hospital Colorado or Spring Harbor Hospital, ME).

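### The recently hospitalised subgroup is planned from Maine alone but compared with children from both sites without a site term, so part of any site difference in the riding effect enters the exploratory hospitalisation contrast

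*Protocol*

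**What the plan says.** Specific Aim 3 names as its third comparison group the "most severely impaired subsample (n = 20) of the THR study population randomized following psychiatric hospitalization". The Setting section gives the source of these children: "the Maine site will also recruit ASD youth psychiatrically hospitalized at Spring Harbor Hospital to address exploratory Aim 3c". The Recruitment paragraph agrees: "The Maine Site will recruit participants discharged from" the inpatient and partial psychiatric units of that one hospital. No psychiatric-unit recruitment is assigned to Colorado.

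The other trial participants come from both places: "all THR and BA control interventions and physiological data collection will take place at two Premiere accredited" riding centres, one in Colorado and one in Maine. The Setting section ends with a notice: "Please note Maine site is closed as of December 31, 2023".

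Under Exploratory AIM 3 in the Data Analysis Plan, "we will compare THR effects between these two groups of THR/BA participants by introducing three extra terms in the model for Aim 1". The added terms are an indicator RecentHosp, its interaction with intervention, and the three-way interaction with intervention and time. The Aim 1 model that they extend has time, arm and their interaction as fixed effects. Site is in neither list, and the comparison is not restricted to Maine.

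Site appears in item 2 of Supplementary analyses. There the THR effect is to be tabulated by site, and site and site-by-intervention terms added to the efficacy models.

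**The concern.** The question is whether THR works differently after a recent psychiatric hospitalisation. Randomisation is carried out separately at each site, so each site's own THR-versus-BA difference is protected. Hospitalisation is neither randomised nor a stratification factor.

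If every hospitalised child is in Maine and many comparison children are in Colorado, the two arm effects being compared come partly from different riding centres, with different instructors and horses. Any difference in the THR effect between centres would then be reported, in part, as an effect of hospitalisation. At stake is the meaning of one exploratory contrast and its 95% confidence interval. The main efficacy analysis is not affected.

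**Working it through.** The protocol gives no figure for this contrast, so there is none to reproduce.

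**Inputs from the protocol**
- 142 THR/BA participants, 71 per arm (Power analysis).
- 20 recently hospitalised children (Specific Aim 3), planned from Maine (Setting). That leaves 142 − 20 = 122 comparators.
- At least 40 Colorado THR/BA participants: two thirds of the first 60, randomised 1:1:1 (Power analysis).

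**Assumptions**
- The site split is not stated, so Colorado is taken as 40, 71 or 90.
- Arms are balanced within each group, with the 20 hospitalised children split 10 and 10. Aim 3 could also be read as meaning THR children only, but the analysis text speaks of THR/BA participants.
- Change scores have SD 1. The contrast is the intended one, a difference between two arm effects on change. This needs a RecentHosp-by-time term, or a factor coding that absorbs it; the term is not among the three listed. The consequences of that omission were not calculated.

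**Bias.** Let D_M and D_C be the THR effect in non-hospitalised children in Maine and Colorado, h the true extra effect of hospitalisation, and q the Colorado share of the comparators.
- Hospitalised group: D_M + h
- Comparators pooled: (1 − q)·D_M + q·D_C
- Contrast: h + q·(D_M − D_C)

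The bias is q times the site difference.

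**Standard error.** Without site: sqrt(2/10 + 2/61) = 0.48. With 112 completers (56 per arm), all 20 hospitalised children retained: sqrt(2/10 + 2/46) = 0.49. With site and its interactions, only Maine comparators inform the contrast: sqrt(4/20 + 4/m), where m is the number of Maine comparators.

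| Colorado | q | Bias, site difference 0.30 SD | Maine comparators m | SE with site terms |
|---|---|---|---|---|
| 40 | 40/122 = 0.33 | 0.10 | 82 | 0.50 |
| 71 | 71/122 = 0.58 | 0.17 | 51 | 0.53 |
| 90 | 90/122 = 0.74 | 0.22 | 32 | 0.57 |

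**Simulation check** (4,000 runs per scenario, no true hospitalisation effect). At a 0.30 SD site difference the mean bias without site was 0.105, 0.179 and 0.213 SD, with false-positive rates of 5.6%, 6.4% and 7.0%. As an extreme, a site difference equal to the whole planning effect (0.62 SD) gave false-positive rates of 5.7%, 10.0% and 14.7%. With site and site by intervention on change scores, which corresponds to site by intervention by time in the mixed model, the bias lay between −0.02 and 0.01 SD and the rate between 4.6% and 5.6%.

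**Least favourable cost.** With completers only and 80% of the 92 comparators from Colorado, 92 × 0.20 / 2 = 9.2 Maine comparators per arm remain. The SE is sqrt(2/10 + 2/9.2) = 0.65.

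**The case against.** Four points count against making much of this.

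**The aim is exploratory.** The protocol describes Aim 3 as hypothesis generating and attaches no formal hypothesis to this contrast. With an SE near 0.49 the 95% interval is about ±0.96 SD whether or not site is modelled. This stands and limits severity.

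**Adjustment trades bias for variance.** The adjusted estimate has the smaller mean squared error only when q²·(site difference)² exceeds 4/m − 4/122. For the three splits that needs a site difference above about 0.39, 0.37 and 0.41 SD. At 0.30 SD the unadjusted estimate is slightly better on that measure. This also stands. The gain is that the adjusted interval answers the stated question, which is a reason to report both.

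**Site is already examined.** Supplementary item 2 could be read as covering the RecentHosp model, and its by-site table would help a reader. But it is a separate analysis of the efficacy models, and nothing places its terms in this contrast. Read literally, its terms also lack site by intervention by time, whereas the THR effect in these models is the arm-by-time term. The Aim 3 sentence on adjusting for imbalanced confounders precedes the hospitalisation model. At most it would add a site main effect, which does not remove a site difference in the THR effect.

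**The sites share a manual, fidelity ratings and accreditation.** These may narrow site differences; they do not show that there are none.

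Three stronger readings are tempting but unsupported. A reader might infer that hospitalisation and site are wholly confounded; the leak is only the Colorado share, because Maine also recruits children from the community. A reader might take the planning effect of 0.62 and the 1.08 from the 16-child pilot at the Colorado centre as evidence of a site difference; neither is a Maine estimate, and the pilot had eight children per arm. A reader might suppose that hospitalised Colorado children would be coded as not hospitalised; RecentHosp is defined by hospitalisation, not by site, so no such error is shown. Maine's closure could raise the Colorado share, but the protocol does not say how many children enrolled afterwards.

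**Conclusion.** The point holds in a limited form. As written, the model passes a fraction of any site difference in the THR effect into the RecentHosp contrast. On the assumed counts that fraction is about 33% to 74%. A site difference of 0.30 SD, which is an assumption, would give a bias of about 0.10 to 0.22 SD, less than half of the contrast's standard error. The result rests on the hospitalised children all being in Maine, which is the plan but not a rule; a hospitalised Colorado child would weaken the link. Severity is low to modest.

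**What to change.** In the Exploratory AIM 3 text, add site, site by time, site by intervention and site by intervention by time to the RecentHosp model, and report this result beside the unadjusted contrast. If all hospitalised children are from Maine, the adjusted estimate equals a within-Maine comparison, provided that RecentHosp by time is also in the model; state that term explicitly.

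The change is to analysis wording and uses data already collected. The cost is precision: the SE rises from about 0.49 to 0.50–0.57 on the assumed splits, and to about 0.65 if only completers are analysed and 80% of comparators are from Colorado.

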General consideration of statistical analysis: Prior to the start of any formal analyses, data for each variable will be examined to identify unusual values that need to be queried, including outliers, patterns of missing values, and non-Gaussian distributions (i.e., have significant skewness and kurtosis). Baseline demographic and clinical characteristics will be summarized using descriptive statistics and grouped by intervention arms. Between-arm difference in demography and baseline variables will be examined using t-test or chi square test respectively for continuous and categorical variables. Any imbalance that could potentially be a confounding factor for the outcome will be adjusted for in statistical models (see below). The primary efficacy analysis will use the “intent-to-treat (ITT)” principle to test our study hypotheses under practical and realistic conditions where not all participants follow or complete the program. All randomized participants will be analyzed in the ITT analyses. Linear Mixed Effect Model (LMM) will serve as the primary method to handle missing values. Other analyses such as completer analysis and analyses with imputed data will be deemed as sensitivity analysis for efficacy examination. However, for mediation analysis, only participants with both the

mediator (intervening) variable and outcome variables available will be included to explore mechanism of the intervention effect. No interim analysis will be conducted. In all analyses, a $p \leq 0.05$ will be considered significant. SAS and Mplus software will be used for these analyses.

AIM1: Efficacy assessment (for H1a-1c): LMM with unstructured covariance will be used to model baseline and end of treatment (EoT or T_2) primary and secondary outcome measures as well as expanded outcomes where fixed effects include evaluation time (baseline or EoT) and intervention arm indicator (THR/BA), as well as their interaction.

[figure not shown]
Estimate of the interaction will be used to quantify effect size and tested for statistical significance.

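### The irritability effect size of 0.62 does not follow from the means, SEMs and Ns printed with it; they give 0.52, and the stated 90% and 97% powers fall with it

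*Protocol*

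**What the plan says.** The Power analysis paragraph (Protocol, Data Analysis Plan) explains that the trial is sized mainly on ABC-C irritability, because mediation can be examined only if there is an intervention effect. The planning effect is taken from the earlier randomised trial, in the subgroup with a psychiatric diagnosis ("N=27 for THR and N=26 for BA, data not published"). The data are given as "The irritability score decreased by 6.9 (1.66 SEM) in the THR group and 2.3 (1.8 SEM) in the BA group", followed directly by "resulting in a Cohen's d of 0.62 for efficacy".

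On enrolment the paragraph says "We will enroll 142 participants (71 per arm"), and it allows for "20% attrition (which is 1% higher than that in our previous trial"), leaving 56 per arm for the completer and mediation analyses. It then concludes that "we will have 97% power at 5% significance to detect significance of THR efficacy for ITT analysis (Aim1) and 90% power for completer analysis". Table 2 repeats 97 and 90 in its irritability row, under columns headed 81 per arm (ITT) and 56 per arm (completers).

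The planned test is the arm-by-time term of a linear mixed model on baseline and end of treatment. Under AIM1, Efficacy assessment: "Estimate of the interaction will be used to quantify effect size and tested for statistical significance".

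**The concern.** The effect size is presented as the result of figures printed in the same sentence, so a reader can check it, and it does not come out. The difference in mean change is 4.6 points. A d of 0.62 therefore needs an SD of about 7.4, which is smaller than the SD of change that the printed SEM and N imply in either arm.

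Much depends on this number. The Mediation section tests path a only for outcomes that are significant on path c. Aim 2 is likewise confined to outcomes found significant in Aim 1. If the planning effect is overstated, the chance of passing the first gate is overstated too, and the later aims depend on passing it.

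**Working it through.** **Inputs** (Protocol, Power analysis): mean decreases 6.9 and 2.3; SEMs 1.66 and 1.8; N = 27 and 26; stated d = 0.62; 71 enrolled and 56 completing per arm; 81 per arm in the Table 2 heading; 5% significance. Sidedness is not stated. Two-sided is assumed because it reproduces the Protocol's own powers.

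**1. Reproduce the stated powers from d = 0.62.** Two-sample t-test, non-central t, non-centrality d × √(n/2):

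- 56 per arm: 90.2% (stated 90%)
- 81 per arm: 97.5% (stated 97%)
- 71 per arm: 95.6%

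The same method reproduces the six-month figures in that section: d = 0.45 gives 81.2% at 81 per arm (stated 81%) and 56.0% at 45 per arm (stated 56%). The power step is therefore sound, and 0.62 is the value that was used.

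**2. Derive d from the printed data.** SD = SEM × √N.

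- THR: 1.66 × √27 = 8.63
- BA: 1.8 × √26 = 9.18
- Pooled: √[(26 × 8.63² + 25 × 9.18²)/51] = 8.90
- d = (6.9 − 2.3)/8.90 = 4.6/8.90 = 0.517

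The SD needed for 0.62 is 4.6/0.62 = 7.42.

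**3. Look for a reading that gives 0.62.**

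| Reading | d |
|---|---|
| Pooled SD, as printed | 0.517 |
| Least to most favourable rounding of every printed figure | 0.498 to 0.537 |
| THR SD alone | 0.533 |
| BA SD alone | 0.501 |
| Small-sample (Hedges) correction | 0.509 |
| SEMs based on 22 and 21 observed (assumption: 19% attrition, as 27 × 0.81 and 26 × 0.81) | 0.574 |
| SEMs based on 19 per arm | 0.610 |
| SEMs based on 18 per arm | 0.626 |

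With equal arms, 0.62 is reached only at about 18 per arm, roughly a third fewer than printed.

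**4. Power at d = 0.517** (two-sided 5%, t-test):

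| Per arm | d = 0.62 | d = 0.517 |
|---|---|---|
| 56 (completers) | 90.2% | 77.4% (74.2–80.4% over rounding) |
| 71 (enrolled, no dropout) | 95.6% | 86.4% |
| 81 (Table 2 heading) | 97.5% | 90.5% |

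With the 22/21 assumption (d = 0.574), power at 56 per arm is 85.3%. One-sided testing at d = 0.517 gives 86% at 56 per arm and 95% at 81 per arm, still short of 90% and 97%.

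**5. Power of the planned mixed model.** Assume two time points, equal variances, data missing at random, 71 per arm at baseline and 56 at end of treatment. The variance of mean change comes from the inverse information matrix, and the effective n per arm is the number of complete pairs with the same precision. Power uses t with 110 df. The baseline-to-end correlation ρ is not given, so a range is shown.

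| ρ (assumed) | Effective n per arm | Power, d = 0.517 | Power, d = 0.62 |
|---|---|---|---|
| 0 | 62.6 | 81.8% | 93.0% |
| 0.5 | 59.1 | 79.5% | 91.6% |
| 0.9 | 56.6 | 77.8% | 90.5% |

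**The case against.** **The Ns may not be the denominators of the SEMs.** The 27 and 26 are described as the participants with a psychiatric diagnosis, not as those with end-of-treatment data. If 20 THR and 17 BA participants were observed, then 1.66 × √20 = 7.42, 1.8 × √17 = 7.42, and d = 0.62 exactly. On that reading the effect size and its powers stand, and only the N label is at fault. This cannot be excluded, because the source data are unpublished. But those counts appear nowhere in the Protocol, and they imply 16 of 53 missing (30%) against the roughly 19% implied for the earlier trial. They would also still leave a printed figure to correct.

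**A different standardiser may have been used**, such as a baseline SD near 7.4. None is named, and the sentence presents 0.62 as following from the printed changes and SEMs. It would not support the power either: with two time points, the precision of the arm-by-time term depends on the SD of change.

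**More participants may be enrolled.** The Protocol elsewhere allows up to 250 youth. If all 250 were randomised 1:1 (an assumption), d = 0.517 would give 98.3% at 125 per arm and 95.3% at 100 per arm after 20% attrition. But 250 is a ceiling, and the stated powers are tied to 142 enrolled and 56 completers per arm. What stands is that the lower powers here hold for those sizes and are not a forecast for a larger trial.

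**Mediation power is separate.** The 90% for the indirect effect comes from a Sobel calculation with its own coefficients and does not use 0.62. The 77% is the between-arm test in completers and does not replace that figure. The link is only the path-c gate.

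**Conclusion.** The point holds. The printed means, SEMs and Ns give d = 0.52 (0.50 to 0.54 over rounding), not 0.62, so the 90% and 97% irritability powers do not follow from the data offered for them.

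If the means, SEMs and Ns are right, completer power at 56 per arm is about 77% instead of 90%, and the chance of missing the effect rises from about 10% to about 23%. Power at 81 per arm is 90.5% instead of 97%. The mixed model with 71 randomised and 56 observed per arm has about 78–82%. These figures assume a two-sided 5% test and the stated enrolment and attrition; the mixed-model range also assumes data missing at random and equal variances.

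The Protocol does not show which printed figure is at fault. If the SEMs rest on fewer observed participants, the gap narrows: d is 0.57 with 22 and 21. The separate mismatch between 71 and 81 per arm does not alter the conclusion, since d = 0.52 misses 97% at either size.

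**What to change.** In the Power analysis paragraph:

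- Go back to the source data and correct whichever of d, the SEMs or the Ns is wrong.
- State whether 27 and 26 are randomised or observed participants.
- Compute d from the SD of change and name that SD, since the planned test is the arm-by-time interaction.
- Restate the irritability powers in the text and in the irritability row of Table 2, each with the n it refers to. If the printed means, SEMs and Ns stand, the values are about 77% for completers at 56 per arm, 90.5% at 81 per arm, and about 78–82% for the mixed model with 71 randomised and 56 observed per arm.

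The cost is one reworded paragraph, one table row and possibly a less favourable stated power. The analysis does not change and no further enrolment is asked for.
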